	
minimal focal inflammation after administration of 100 mg/kg. Immune complex disease was not observed in the 6-month repeat dose (2 doses) study at the same doses. It is unknown whether immunogenicity in humans after dosing will result in the formation of pathogenic immune complexes as data from preclinical models is not necessarily predictive of immune complex disease in human effects.
	
low C3 or low C4), previous history of vasculitis and patients with a significantly elevated Alanine aminotransferase (ALT) or history of liver disease.
 
 ▪ Safety evaluation of individual participants will be in place, with data being reviewed on an ongoing basis by the Sponsor and Investigators. Any clinical signs that might indicate immune complex disease will be reported to the sponsor's medical monitor within 24 hours of the investigator becoming aware of the event, regardless whether the event is considered serious or non-serious. Participants will be investigated and treated as clinically indicated (Appendix 3). ▪ Targeted monitoring of laboratory data (tests shown in Section 7.3.6 and time points shown in Section 7.1) will include urinalysis to detect haematuria and microalbuminuria and clinical chemistry parameters. ADA and immune complex concentrations, trends in C3 and C4, platelets and inflammatory markers, over time will also be assessed. ▪ Halting and monitoring rules, based on the clinical findings, are defined to minimise the risk to participants (Section 5.4 and Section 5.5).

Potential Risk of Clinical Significance	Summary of Data/Rationale for Risk	Mitigation Strategy

 ▪ Immunogenicity, ADAs 	
 ▪ Biopharmaceutical products may elicit ADAs, which have the potential to modulate PK or PD, or to produce adverse reactions. This is the GSK3511294 FTIH study, hence the ADA response in humans is unknown. 	
 ▪ A single dose of GSK3511294 will be administered to a participant. ▪ Binding ADAs to GSK3511294 will be measured, and adverse event profile will be compared between ADA-positive and ADA-negative participants.

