5.4.2. Criteria for follow up of potential Type III Hypersensitivity/Immune Complex Disease

Owing to the adverse effects consistent with immune complex disease, that were observed in the 1-month, but not 6-month, monkey studies, events consistent with type III hypersensitivity/immune complex disease will be reported to the GSK medical monitor within 24 hours of the Investigator becoming aware of the event, regardless whether the event is considered serious or non-serious. Treatment for the event will be given as medically required (see [Appendix 3](#) regarding proposed management). If possible, PK, ADA and CIC samples should be taken at the time of the event.

- A combination of general symptoms associated with hypersensitivity or other potential clinical manifestations of immune complex disease. Symptoms include but are not limited to:
 - persistent* fever
 - persistent* muscle and joint pain
 - persistent* rash
 - symptoms of peripheral neuropathy, like numbness or weakness, and associated with progressive decrease in complement markers (C3, C4)
- * Persistent is considered to be longer than 2 days.
- Urticaria.
- Clinical symptoms suggestive of serum sickness (e.g., fever, general ill feeling, hives, itching, joint pain, rash, swollen lymph nodes).
- Persistent thrombocytopenia, elevated hsCRP, or kidney or liver function tests indicative of organ damage:

- reduced platelet count
- elevated hsCRP
- elevated serum creatinine
- urinary albumin-creatinine ratio > 3 mg/mmol in the absence of a urinary tract infection
- persisting urinalysis abnormality for longer than 1 week
- macroscopic haematuria, without a clear cause (such as trauma)
- Participants who experience any of the above events will be withdrawn from the study (ie they won't take part in further study procedures, if clinically indicated; however, they will be followed up for safety, as required). If the participant is well enough to do so, they may continue in the study.

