7.1. Time and Events Table

Procedure	Pre-Screen 1	Screen 2	In-Patient Period ^{3,4}							Out-patient Visits ^{4,5}													
			Day -1	Day 1			Day 2	Day 3	Day 4	Week													
				Pre-dose	0	2 h	8 h	24 h	48 h	72 h	NA	1	2	4	8	12	18	24	26	32 ⁵	36 ⁵	40 ⁵	
				5	8	15	29	57	85	127	169	183	225 ⁵	253 ⁵	281 ⁵	Day							
Haematology (including blood eosinophil count), Clin. Chem., Urinalysis and hsCRP		X	X					X	X	X	X	X	X	X	X	X	X	X	X	X	X	X	
Serum save (for immunological analysis, if needed)		X																					
Inflammatory markers		X																					
Complement (C3 & C4)		X	X					X	X	X	X	X	X	X	X	X	X	X	X	X	X	X	
Total IgE			X					X	X	X	X		X	X	X	X	X	X	X	X	X	X	
PK Blood Samples																							
Immunogenicity				X									X	X	X	X	X	X	X	X	X	X	
CICs				X				X					X	X	X	X	X	X	X	X	X	X	
12-lead ECG ¹⁴		X	X	X		X	X	X	X	X	X	X	X	X	X	X	X	X	X	X	X	X	
Vital signs ¹⁵		X	X	X		X	X	X	X	X	X	X	X	X	X	X	X	X	X	X	X	X	
AE/SAE review (inc local ISR up to 72 h after dosing)				X	¹⁶																		
IL-5 sample			X										X	X		X	X	X	X	X	X	X	
Exploratory biomarkers of asthma in blood			X												X			X					
Spirometry		X	X			X		X		X		X		X		X				X	X	X	
PEF Training ¹⁷		X																					
PEF ¹⁷													X	¹⁷									
Diary review ¹⁷													X	X	X	X	X	X	X	X	X	X	

Abbreviations: ACT = Asthma Control Test; AE = adverse event; BMI = body mass index; CICs = circulating immune complexes; CRP = C-reactive protein; ECG = electrocardiogram; FSH = follicle stimulating hormone; h = hour(s); Hep B = Hepatitis B; Hep C = Hepatitis C; HIV = human immunodeficiency virus; IgE = immunoglobulin E; IL-5 = interleukin-5; IP = Investigational Product; ISR = injection site reactions; PEF = peak expiratory flow; PK = pharmacokinetic; SABA = short acting β -agonist; SAE = serious adverse event.

Notes:

1. Pre-screen up to 12 weeks before dosing. Blood eosinophils must be ≥ 200 cells/ μ L for participants to proceed to screening. Blood eosinophil count may be existing data or obtained at a pre-screen visit.
2. Screening up to 4 weeks before randomisation. Screening procedures may be done at one or more visits, within the screening window.
3. In the UK, all participants will be in-patient for at least 72 h after dosing. In Germany, all participants will be in-patient for at least 8 days after dosing (see [Appendix 8](#) for the German-specific time and events table).
4. Allowed time deviations will be documented in the Study Reference Manual.

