7.3. Safety

Planned time points for all safety assessments are listed in the Time and Events Table (Section 7.1). Additional time points for safety tests (such as vital signs, physical exams and laboratory safety tests) may be added during the course of the study based on newly available data to ensure appropriate safety monitoring.

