	RBC Count		MCV	WBC	
				Neutrophils	
	Haemoglobin		MCH	Lymphocytes	
	Haematocrit			Monocytes	
				Eosinophils	
				Basophils	
Clinical Chemistry	BUN	Potassium	AST (SGOT)		
	Creatinine	Sodium	ALT (SGPT)		
	Glucose (fasted at screening)	Calcium	Alkaline phosphatase	Albumin	
		Magnesium			
Routine Urinalysis	
 Specific gravity pH, glucose, protein, blood and ketones by dipstick Microscopic examination and UACR (if blood or protein is abnormal [evidence of microalbuminuria or haematuria of $\geq 1+$]) 				
Other tests	
 hsCRP 				
Other Screening Tests	
 HIV Hepatitis B (HBsAg; in Germany only, anti-HBc will also be tested [Appendix 8]) Hepatitis C (Hep C antibody) FSH and estradiol (if required to confirm postmenopausal status) Alcohol, cotinine and drug screen (to include at minimum: amphetamines, barbiturates, cocaine, opiates, cannabinoids and benzodiazepines) 				

Abbreviations: ALT (SGPT) = alanine aminotransferase (serum glutamic pyruvic transaminase); AST (SGOT) = aspartate aminotransferase (serum glutamic oxaloacetic transaminase); BUN = blood urea nitrogen; FSH = follicle stimulating hormone; HBsAg = hepatitis B surface antigen; anti-HBc = hepatitis B core antibody; hsCRP = highly sensitive C-reactive protein; MCH = mean corpuscular haemoglobin; MCV = mean corpuscular volume; RBC = red blood cell; UACR = urinary albumin-creatinine ratio; WBC = white blood cell, pH= hydrogen ion concentration.

1. The following post-dose results will be blinded to Investigators and blinded Sponsor representatives: total WBCs; absolute and percentage eosinophils; and percentage neutrophils, lymphocytes, monocytes and basophils.

All laboratory tests with values that are considered clinically significantly abnormal during participation in the study or within the defined in clinic follow up periods should be repeated until the values return to normal or baseline. If such values do not return to normal within a period judged reasonable by the investigator, the etiology should be identified and the sponsor notified.

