
MONITORING:
 
If $\text{ALT} \geq 3 \times \text{ULN}$ AND $\text{bilirubin} \geq 2 \times \text{ULN}$ or $\text{INR} > 1.5$:
 
 Repeat liver chemistries (include ALT, AST, alkaline phosphatase, bilirubin) and perform liver event follow up assessments within 24 hours Monitor participants twice weekly until liver chemistries resolve, stabilise or return to within baseline A specialist or hepatology consultation is recommended 
If $\text{ALT} \geq 3 \times \text{ULN}$ AND $\text{bilirubin} < 2 \times \text{ULN}$ and $\text{INR} \leq 1.5$:
 
 Repeat liver chemistries (include ALT, AST, alkaline phosphatase, bilirubin) and perform liver event follow up assessments within 24-72 hours Monitor participants weekly until liver chemistries resolve, stabilise or return to within baseline 	
If $\text{ALT} \geq 3 \times \text{ULN}$ AND $\text{bilirubin} \geq 2 \times \text{ULN}$ or $\text{INR} > 1.5$:
 
 Anti-nuclear antibody, anti-smooth muscle antibody, Type 1 anti-liver kidney microsomal antibodies, and quantitative total immunoglobulin G (IgG or gamma globulins). Serum acetaminophen adduct High-performance liquid chromatography (HPLC) assay (quantifies potential acetaminophen contribution to liver injury in participants with definite or likely acetaminophen use in the preceding week [James, 2009]). Liver imaging (ultrasound, magnetic resonance, or computerised tomography) and /or liver biopsy to evaluate liver disease: complete Liver Imaging and/or Liver Biopsy CRF forms.

1. Serum bilirubin fractionation should be performed if testing is available. If serum bilirubin fractionation testing is unavailable, **record presence of detectable urinary bilirubin on dipstick**, indicating direct bilirubin elevations and suggesting liver injury.
2. All events of $\text{ALT} \geq 3 \times \text{ULN}$ and $\text{bilirubin} \geq 2 \times \text{ULN}$ ($>35\%$ direct bilirubin) or $\text{ALT} \geq 3 \times \text{ULN}$ and $\text{INR} > 1.5$, if INR measured, which may indicate severe liver injury (possible 'Hy's Law'), must be reported as an SAE (excluding studies of hepatic impairment or cirrhosis).

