
f. Other situations:
 
 Medical or scientific judgment should be exercised in deciding whether reporting is appropriate in other situations, such as important medical events that may not be immediately life-threatening or result in death or hospitalization but may jeopardise the participant or may require medical or surgical intervention to prevent one of the other outcomes listed in the above definition. These should also be considered serious. Examples of such events are invasive or malignant cancers, intensive treatment in an emergency room or at home for allergic bronchospasm, blood dyscrasias or convulsions that do not result in hospitalization, or development of drug dependency or drug abuse

g. Is associated with liver injury and impaired liver function defined as:
 
 ALT \geq 3xULN and total bilirubin* \geq 2xULN (>35% direct), or ALT \geq 3xULN and INR** $>$ 1.5. 
* Serum bilirubin fractionation should be performed if testing is available; if unavailable, measure urinary bilirubin via dipstick. If fractionation is unavailable and ALT \geq 3xULN and total bilirubin \geq 2xULN, then the event is still to be reported as an SAE.
 
** INR testing not required per protocol and the threshold value does not apply to participants receiving anticoagulants. If INR measurement is obtained, the value is to be recorded on the SAE form.

 Refer to Appendix 2 for the required liver chemistry follow-up instructions

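### Does running the urinary albumin-creatinine ratio only after an abnormal urine test leave the Section 5.4.2 renal criterion unworkable?

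*Protocol*

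**What the plan says.** Four parts of the protocol bear on this.

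- **Section 5.4.2** lists events to be reported to the medical monitor within 24 hours as possible type III hypersensitivity or immune complex disease. One is "urinary albumin-creatinine ratio > 3 mg/mmol in the absence of a urinary tract infection". It is a sub-item under a line on persistent thrombocytopenia, raised hsCRP, or kidney or liver tests that point to organ damage. The section continues: "Participants who experience any of the above events will be withdrawn from the study". It qualifies this by clinical indication and lets a participant who is well enough stay in.
- **Section 4.7.1** says that laboratory monitoring for this risk "will include urinalysis to detect haematuria and microalbuminuria and clinical chemistry parameters".
- **Section 7.3.6, Table 5** tests urine protein and blood by dipstick. It then adds "Microscopic examination and UACR (if blood or protein is abnormal", with a bracket naming microalbuminuria or haematuria and a 1+ cut-off.
- **Section 7.1** schedules urinalysis within one combined row, "Haematology (including blood eosinophil count), Clin. Chem., Urinalysis and hsCRP". The rows shown contain no separate UACR.

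**The concern.** The criterion in Section 5.4.2 has one qualifier, the absence of a urinary tract infection. Nothing there says that the value exists only after an abnormal dipstick. In a participant with low-grade albuminuria, a negative dipstick and no other trigger, the planned tests never produce the number, and a criterion that was not measured could be read as not met. The 24-hour report would then not start from it.

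The risk is a named one. Section 4.7.1 puts the kidney first among the organs concerned, and the monkey finding behind it (Section 2.2) included the kidney. The gate also looks partly circular: microalbuminuria is a condition for running UACR, yet the only planned urine protein test before it is the dipstick. It is unclear whether the 1+ cut-off applies to haematuria alone or to both findings. Finally, the protocol seems more careful about INR, another conditional test: Section 12.5.2 states "INR testing not required per protocol and the threshold value does not apply to participants receiving anticoagulants", and Appendix 2 adds "if INR measured, which may indicate severe liver injury".

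**Working it through.** The protocol states no figure on this point, so the check is mainly a comparison of text, followed by the arithmetic that bounds its size.

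**1. Do the sections contradict each other?** Section 5.4.2 fixes what happens when a UACR result exceeds 3 mg/mmol. Table 5 fixes when a UACR is run, and Section 7.3.6 makes Table 5 the definition of the required laboratory tests. Both can be followed at once. Section 4.7.1 says urinalysis is there to find haematuria and microalbuminuria, and the Table 5 gate names the same two findings.

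**2. Is INR handled differently?** Section 5.4.3.1 lists INR above 1.5 with no caveat. The caveats stand elsewhere, in Section 12.5.2 and Appendix 2. UACR has the same layout: threshold in Section 5.4.2, testing condition in Table 5.

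**3. How large could the gap be?** At the threshold, albumin (mg/L) = 3 mg/mmol × urine creatinine (mmol/L). A strip that turns abnormal at L mg/L can miss a value above the threshold only when creatinine is below L/3. The protocol gives neither L nor creatinine. Assume creatinine of 3 to 30 mmol/L, so the threshold is 3 × 3 = 9 to 3 × 30 = 90 mg/L.

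| Strip turns abnormal at (mg/L) | Gap where creatinine is below (mmol/L) | Part of the assumed span |
|---|---|---|
| 9 | 9/3 = 3 | none |
| 45 | 45/3 = 15 | creatinine 3 to 15 |
| 90 | 90/3 = 30 | all of it; the same for any higher limit |

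Abnormal dipstick blood also triggers UACR, so the real gap is no larger than this and may be smaller.

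**4. What might it do to the chance of seeing a case?** Section 9.2.1 uses 1 − (1 − p)^n. At a 20% rate this gives 1 − 0.8^6 = 73.8% for 6 participants and 1 − 0.8^9 = 86.6% for 9, matching the stated 74% and 87%. Let s be the share of participants above the UACR threshold who also have an abnormal dipstick, and replace p by s × p. With n = 6 the chance is 73.8% at s = 1, 46.9% at s = 0.5 and 0% at s = 0. The protocol does not give s, so this is an illustration and not an estimate.

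**5. What would UACR at every urinalysis require?** The Section 7.1 row has 2 pre-dose and 12 post-dose urinalyses to Week 26, plus 1 later visit (2 to 100 mg) or 2 (300 mg): 15 or 16 per participant. For 48 participants: 40 × 15 + 8 × 16 = 728. The German schedule adds Day 9; if all followed it, 40 × 16 + 8 × 17 = 776. At the maximum of 72, the 24 extra participants at 15 to 17 each give 728 + 360 = 1,088 to 776 + 408 = 1,184. Screen failures and replacements are not counted.

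**The case for a change.** The strongest case for a change is that Section 5.4.2 already lists a urinalysis abnormality lasting more than a week. Dipstick-positive participants whose finding persists are caught there, so tying UACR to the dipstick removes the cases that only UACR could add. Appendix 3 does not name UACR among its extra samples, and the other routes to it are discretionary. A silent finding may prompt none of them.

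Part of this stands. In a dipstick-negative participant no UACR is planned, and the wording of Section 5.4.2 does not say so. But the follow-on test is not redundant: it gives a quantitative result at the first abnormal dipstick, without waiting a week, and it also runs when only blood is abnormal. The hardest example, an isolated raised UACR, is also not clearly what Section 5.4.2 targets, since the item sits under tests that point to organ damage.

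Nor does monitoring of this risk rest on UACR. Serum creatinine, platelets and hsCRP are measured at the same visits as urinalysis, and complement and circulating immune complexes are scheduled. A test can be added when wanted: "Additional time points for safety tests (such as vital signs, physical exams and laboratory safety tests) may be added" during the study (Section 7.3), and Section 12.5.5 obliges the investigator to arrange supplemental tests for an adverse event where indicated. What counts as abnormal protein is also not left wholly open, because Section 7.3.6 has the laboratory supply reference ranges for all safety parameters.

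**Conclusion.** No change to the plan follows. The textual observation is accurate, but it describes an ordinary follow-on test whose condition is stated in Table 5 and not repeated in Section 5.4.2. Cross-referring the two sections, or clarifying what the 1+ bracket covers, would tidy the text without altering anything the trial does.

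The alternative, UACR at all 15 to 17 urinalyses per participant, is a real choice with a real downside. It would bring isolated raised values into the 24-hour reporting and the withdrawal or continuation provision of Section 5.4.2. Where there is ongoing clinical concern, it would also bear on the escalation limit in Section 4.3. Weighing that is a clinical decision for the sponsor, and the document does not show the present choice to be wrong.

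The size of any detection gap is unknown, and the range includes zero. It rests on an assumed creatinine span of 3 to 30 mmol/L and on a strip whose sensitivity the protocol does not state; the Laboratory Manual, not seen here, may specify it. If the strip proved insensitive across that span, the trade-off would deserve a fresh look.

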7.3.7. Lung function tests

FEV₁, FVC and PEF will be measured, as described in the SRM.

7.4. Pharmacokinetics

7.4.1. Blood Sample Collection

Blood samples for determination of GSK3511294 plasma concentration will be collected at the time points indicated in [Table 4](#).

The actual date and time of each blood sample collection will be recorded. The timing of PK samples may be altered and/or PK samples may be obtained at additional time points to ensure thorough PK monitoring.

Processing, storage and shipping procedures are provided in the appropriate lab manual.

7.4.2. Sample Analysis

Plasma analysis will be performed under the control of Platform Technology and Science (PTS), GlaxoSmithKline, the details of which will be included in the SRM.

Concentrations of GSK3511294 will be determined in plasma samples using the currently approved bioanalytical methodology. Raw data will be archived at the bioanalytical site (detailed in the SRM).

Once the plasma has been analysed for parent compound any remaining plasma may be analysed for other compound-related material and the results reported under a separate PTS, GlaxoSmithKline protocol.

7.5. Immunogenicity

Samples for testing binding antibodies against GSK3511294 will be collected at the time points indicated in the Time and Events Tables. The actual date and time of each blood sample collection will be recorded. Processing, storage and shipping procedures are provided in the SRM.

Sample analysis will be performed under the control of PTS, GlaxoSmithKline. The presence of anti-GSK3511294 binding antibodies will be determined in serum samples using a validated bioanalytical method, which includes a screening assay, confirmation assay and titre analysis. If necessary, further immune response characterization may be performed as needed.

7.6. Circulating Immune Complexes

Samples for circulating immune complexes (CIC) will be collected at the time points indicated in the Time and Events Tables. The actual date and time of each blood sample collection will be recorded. Processing, storage and shipping procedures are provided in the SRM.

Sample analysis will be performed under the control of PTS, GlaxoSmithKline. The presence of CICs will be determined in serum samples using a validated bioanalytical assay, using immunoglobulin detection. Further characterization with drug specific detection may be performed as needed.

7.7. Complement, IgE and inflammatory markers

Blood samples will be collected during the study to measure complement (C3 and C4) and total IgE. Assessments will be performed by a central laboratory.

Inflammatory markers at screening will comprise Tumour necrosis factor-alpha (TNF- α), IL-2, IL-6, IL-10, Interferon-gamma (IFN- γ) and C3a. A screening serum sample will also be stored for assay of Antinuclear antibodies (ANA), Anti-neutrophil cytoplasmic antibody (ANCA) and anti-DNA antibodies, if required at a later date based on symptoms. After dosing, additional inflammatory markers and tests will be considered on an ad hoc basis should there be clinical concerns regarding an immune mediated AE (see Section 5.4.2 and [Appendix 3](#)).

Refer to the SRM for appropriate processing and handling of samples to avoid duplicate and/or additional blood draws.

7.8. Pharmacodynamic and Exploratory Markers

7.8.1. Pharmacodynamic Biomarkers

Serum samples will be collected during this study to measure total IL-5 levels as a marker of target engagement. Additionally, blood eosinophil levels will be measured as part of the haematology panel as a marker of pharmacological response. Samples will be collected at the time points indicated in Section 7.1, Time and Events Tables. The timing of the collections may be adjusted on the basis of emerging PK or PD data from this study or other new information in order to ensure optimal evaluation of the biomarker endpoints.

